### **3.4 Study Population**

In the Main RCT, we plan to recruit 4-6 urban practices from CHOP's Pediatric Research Consortium (PeRC) to participate in the study. These practices care for a diverse, complex urban population and have onsite social workers to assist with family crises. Using well-established methods that have proven effective in multiple large-scale trials, 4-6 practices located in Philadelphia will be recruited to participate using letters of invitation and in-person presentations. Incentives to participate will include provider education on early child development and opportunities for families to be eligible to receive patient navigation services. Children will be eligible to participate in the Main RCT if they are <30 months old, >35 weeks estimated gestational age, reside in Philadelphia, present at a CHOP Primary Care practice located in Philadelphia, have parents who speak English or Spanish, and have recently been referred to the Infant Toddler Early Intervention Program in Philadelphia County. Children >30 months old will not be eligible, since they are transitioning to Preschool Early Intervention (Part B services) and have little time for retention or

---

completion of the program. In addition, children outside of Philadelphia County will not be eligible, since they would be referred to EI services in a different county. Children will be excluded if they have received EI services in the past 2 weeks. In our pilot study, this exclusion resulted in 25 of 88 patients (28%) being excluded. A total of 360 eligible children, 90 children/year, will be recruited from participating practices to achieve a diverse sample of children. Based on a previous clinical trial involving the 4 practices, the number of potentially eligible children is estimated at 332/year.

For the COVID-19 Sub-study, one parent from each of the currently enrolled parent-child dyads from the Main RCT, will be eligible to participate. If the parent is a former participant in the main RCT, the parent will only be invited to participate in the sub-study if they had previously provided consent to be contacted for future research in the main RCT's consent [or verbal reconsent] form.

For the Trauma-Informed Co-parenting Sub-study, we plan to recruit and enroll around 100 participants in total; 50 participants (main RCT subject group) and up to 50 experts in parenting, childhood trauma, and/or co-parenting (expert subject group) Parent participants from the currently enrolled parent-child dyads in the Main RCT will be eligible to participate. If the parent is a former participant in the main RCT, the parent will only be invited to participate in the sub-study if they had previously provided consent to be contacted for future research in the main RCT's consent [or verbal reconsent] form.

### **3.4.1 Inclusion Criteria**

#### ***3.4.1.1 Main RCT***

- 1) Child is <30 months old at time of enrollment
- 2) Child was born >35 weeks estimated gestational age
- 3) Parent-child dyad reside in Philadelphia and present at a CHOP primary care practice located in Philadelphia
- 4) Parents are English or Spanish speaking
- 5) Child has recently been referred to the Philadelphia Infant Toddler Early Intervention Program in Philadelphia County

#### ***3.4.1.2 COVID-19 Rapid Response Sub-study***

- 1) Parent is currently enrolled in the Main RCT or, if a former participant in the Main RCT, provided consent to be contacted for future research

#### ***3.4.1.3 Trauma-Informed Co-parenting Sub-study***

##### ***3.4.1.3.1 (Phase 1)***

Recognized expert in parenting, childhood trauma, and/or co-parenting, with a minimum of two peer-review first author manuscripts on the subject matter

### **3.4.1.3.2 (Phase 2)**

- 1) Parent is currently enrolled in the Main RCT or, if a former participant in the Main RCT, provided consent to be contacted for future research
- 2) Parent has an ACEs score of 2 or more
- 3) Parents has a child who is 42 months of age or younger

### **3.4.2 Exclusion Criteria**

#### **3.4.2.1 Main RCT**

- 1) Child moves outside of Philadelphia County
- 2) Child has received EI services in the past 2 weeks
- 3) Child has HIV or congenital anomalies or genetic syndromes that place them at risk of developmental delays

#### **3.4.2.2 COVID-19 Rapid Response Sub-study**

- 1) Parent is no longer enrolled in the Main RCT and has not provided consent to be contacted for future research

#### **3.4.2.3 Trauma-Informed Co-Parenting Sub-Study**

##### **3.4.2.3.1 (Phase 1)**

- 1) Expert has at least 2 peer-reviewed first author manuscripts on the subject matter

##### **3.4.2.3.1 (Phase 2)**

- 1) Parent is no longer enrolled in the Main RCT and has not provided consent to be contacted for future research

Subjects that do not meet all of the enrollment criteria may not be enrolled. Any violations of these criteria must be reported in accordance with CHOP and PDPH IRB Policies and Procedures.

## **4 STUDY PROCEDURES**

### **4.1 Main RCT**

#### **4.1.1 Screening/Enrollment (Baseline) Visit**

- Medical Record Review
- Review of Inclusion/Exclusion Criteria

---

- Informed Consent
- Randomization
- Measures of the following:
- Demographics
- EI Engagement
- Measure of Cognitive Stimulation Provided in the Home (StimQ)
- Short Assessment of Health Literacy (SAHL) [\*Due to the interactive nature of the SAHL measure, in the event that the baseline visit must be conducted remotely, the participant will have the option of either completing the SAHL by utilizing a video conferencing application or completing the SAHL in-person at a later date. As a result, the SAHL is a baseline measure that may be completed during a subsequent follow-up visit. If a visit is conducted using a video conferencing application, we will try to use a HIPAA-compliant application licensed by CHOP (i.e., Skype, Bluejeans or WebEx).]

## 4.2 COVID-19 Rapid Response Sub-study

- Verbal Informed Consent
- Emailed RedCap survey
- Audio-recorded semi-structured telephone interview

## 4.3 Trauma-Informed Co-parenting Sub-study

### 4.3.1 Screening/Enrollment (Baseline) Visit (Phase 1)

- Review of Inclusion/Exclusion Criteria
- Participant selected ‘Yes’ on interest form

### 4.3.2 Screening/Enrollment (Baseline) Visit (Phase 2)

- Review of Inclusion/Exclusion Criteria
- Verbal Informed Consent/HIPAA Authorization

## 4.4 Study Treatment Phase

Over the course of each subject’s participation, the subject will have 3 follow-up visits, and a final study visit. At each of the three follow-up visits, measures of engagement, completion of EI referral, utilization of EI services, and eligibility for initiation of EI services will be collected. An additional measure of developmental outcomes will be

collected at the fourth and final study visit. Participants randomized into the intervention arm are assigned a FN who will carry out regular follow-up check-in sessions with the parents.

#### 4.4.1 Main RCT

##### 4.4.1.1 *3-mo, 6-mo, 9-mo follow up visits*

- EI Engagement
- Measures of the following:
- completion of EI Referral
- use of EI Services
- eligibility for initiation of EI Services (IFSP)
- Measure of experienced adversity (Philadelphia Expanded ACE measure - administered once during the study at the **3-month survey** timepoint; however, can be administered during later study visit if not completed during 3-month survey timepoint)

##### 4.4.1.2 *Final Study Visit (12-mo follow-up)*

- EI Engagement
- Measures of the following:
- completion of EI Referral
- use of EI Services
- eligibility for initiation of EI Services (IFSP)
- BSID-III (\*In the event in-person procedures cannot take place at the time of the final study visit time-point (due to COVID-19 or other reasons) this assessment may be performed beyond the 12-month time-point, at a later date, anytime before the child turns 42 months and 15 days old.)

#### 4.4.2 Trauma-Informed Co-parenting Sub-study

##### 4.4.2.1 *Childhood Trauma and Parenting Expert – Delphi Process*

- Delphi process questionnaire

##### 4.4.2.2 *FF Trauma-Informed Focus Group – Adaptation Phase (Phase 2)*

- Interviews

## 4.5 Unscheduled Visits

Unscheduled visits are not anticipated.

## 4.6 Subject Completion/Withdrawal

Subjects may withdraw from the study at any time without prejudice to their care. They may also be discontinued from the study at the discretion of the Investigator for lack of adherence to the study visit schedule or any AEs. The Investigator may also withdraw subjects who violate the study plan, or to protect the subject for reasons of safety or for administrative reasons. It will be documented whether or not each subject completes the study. If the Investigator becomes aware of any serious, related adverse events after the subject completes or withdraws from the study, they will be recorded in the source documents and on the CRF.

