therefore the variation in time-point of when the ACEs survey is administered is not expected to affect the veracity of the reported responses.

Finally, all children will be assessed for developmental status around 12 months following enrollment at a time before the child turns 42 months 15 days. Parent's and children will have the option of attending the Seashore house on CHOP's main campus or the Robert's Center for Pediatric Research on CHOP's main campus, whichever is most convenient for the participant, to complete a measure of child developmental status (BSID-III) (Appendix 5). If the participant chooses the Seashore House, the Center for Human Phenomic Science will conduct the developmental assessment. If the participant chooses the Robert's Center for Pediatric Research, a clinician will conduct the developmental assessment. In the event in-person procedures cannot take place at the time of the final study visit time-point (due to COVID-19 or other reasons) this assessment may be performed beyond the 12-month time-point, at a later date, anytime before the child turns 42 months and 15 days old. EI data on referral completion, EI referral completion, EI eligibility, and EI services use will be obtained from Philadelphia Infant Toddler Intervention, a community partner on this proposal, to corroborate parent self-report. The Early Intervention data is collected and managed by the Philadelphia Infant and Toddler Early Intervention Program in the Department of Behavioral Health and Intellectual Disabilities Services.

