## 6.3 Control of Bias and Confounding

Randomization and allocation concealment are the primary means of avoiding bias. Analytic strategies will also be used to control for residual confounding: (1) Stratification will control for imbalance not controlled by design. (2) Additional potential confounders will be evaluated for any residual association with treatment and included in model as needed. (3) Post randomization effects: The primary source of bias will arise after randomization from dropout and loss to follow-up. To address this problem and avoid missing data, we shall implement the following measures: (a) incentives to each family to complete the study, (b) collection of multiple contact numbers and tracking of changes, and (c) contact all randomized participants, even if they do not continue with their clinical contacts. Baseline data collection will include questions about factors that predict potential dropout, such as current living situations and regularity of contact with health care providers. (4) Our analytic model for treatment effect will include not only potential confounders but also predictors of dropout, to be able to relax assumptions about the missing data process. (5) To investigate the possibly informative dropout (for reasons related to the intervention), we will implement sensitivity analyses (6) For missing values in any of the outcome measurement tools, we will implement formal methods of multiple imputation. (7) We shall account for all dropouts and check all baseline information in real time for both invalid values and missing items and then prompt the child's caregiver for any corrections or clarifications. Then, if any covariates remain missing, we shall implement multiple imputation. (8) Attenuation bias from non-compliance might also occur if the child remains

in the study but fails to adhere to all aspects of the intervention. To address this potential problem, and to estimate the effect of treatment in the presence of full compliance, we will implement the methods outlined by Small and colleagues and by Nagelkerke. However, the “as randomized” approach will remain the primary method for assessing statistical significance of the intervention.

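### Protocol section 4.6 lets randomised families be discontinued for missed visits without keeping outcome collection going, which could create or worsen arm-related missing outcomes

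*Protocol*

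**What the plan says.** **Removal.** Protocol section 4.6 says that a subject may be "discontinued from the study at the discretion of the Investigator for lack of adherence to the study visit schedule". It goes further: "The Investigator may also withdraw subjects who violate the study plan", and withdrawal for safety or administrative reasons is also allowed. What the subject leaves is the study, not only contact with the navigator. Section 4.6.1, although titled as an early termination visit, mentions only follow-up recommendations and referrals. It lists no Bayley assessment and no EI measure.

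**Follow-up of everyone.** Section 3.1.1 plans systematic data collection on every participant and says that "all children will be assessed for developmental status around 12 months following enrollment". Section 5.1.2.1 repeats that every child is assessed. Section 6.3 warns: "The primary source of bias will arise after randomization from dropout and loss to follow-up". Among its countermeasures, the team will "contact all randomized participants, even if they do not continue with their clinical contacts".

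**Dropout by arm.** Section 6.5 expects lower dropout in the intervention arm, because navigation is meant to raise engagement, and plans on a control rate twice the intervention rate.

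**Analysis.** Section 6.3 plans an as-randomised primary analysis, multiple imputation, predictors of dropout in the model, and sensitivity analyses for informative dropout. The SAP says nothing about withdrawal or missing data.

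**County.** The Main RCT exclusion list (3.4.2.1) contains "Child moves outside of Philadelphia County". The inclusion list (3.4.1.1) already requires "Parent-child dyad reside in Philadelphia".

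**The concern.** The intervention works by helping families follow through. Whether a family keeps its study visits is therefore observed after randomisation and may itself depend on arm. A rule that lets the investigator end participation on that ground selects on something that the protocol expects to differ between arms.

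The primary outcome is most exposed, because the Bayley needs the child to attend once, at about 12 months. A family that missed the 3-, 6- and 9-month contacts could still attend, and sections 3.1.1 and 4.4.1.2 allow a late assessment until the child reaches 42 months 15 days. EI outcomes are partly available from agency records, under a release signed at the consent visit (section 9.5.1), with no visit needed. Ending outcome collection for missed visits would give up data that might still be obtained.

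**Working it through.** **1. The passages side by side**

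| Question | Sections 4.6 and 4.6.1 | Sections 3.1.1, 5.1.2.1 and 6.3 |
|---|---|---|
| May a randomised family be ended for missed visits? | Yes, at the investigator's discretion | Data from every participant; everyone randomised is contacted |
| Is the Bayley still done after discontinuation? | Not stated; nothing listed at early termination | Every child is assessed |
| Do EI agency data continue? | Not stated | Agency data obtained to corroborate parent report |

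No text in either document says which side prevails.

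**2. The plan's own retention figures**

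Section 3.2 randomises 360 children 1:1, so 180 per arm. Section 6.5 expects 300 completers, so 60 are lost.

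- Control loss at twice the intervention rate: 60 × 2/3 = 40 controls (40/180 = 22.2%) and 60 × 1/3 = 20 intervention (20/180 = 11.1%), leaving 140 and 160.
- Section 6.5 instead gives about 130 and 170: losses of 50 (50/180 = 27.8%) and 10 (10/180 = 5.6%), a ratio of 5:1.

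The stated split does not reproduce from the stated ratio. That is a separate matter. It means only that the documents give no single baseline for differential loss, so the next step works per 10 percentage points of extra loss.

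**3. Size of the possible shift**

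Let *d* be the share of an arm that is lost, and let lost children score *D* points below those who remain. The full-arm mean is (1 − *d*)·*m* + *d*·(*m* − *D*) = *m* − *dD*, where *m* is the completer mean. The completer mean is therefore too high by *dD*, and

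shift in (intervention − control) = −(*d*_control − *d*_intervention) × *D*.

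Both inputs below are assumptions and neither is in the documents: 10 percentage points of extra control loss, and a gap of 5 to 8 points.

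- *D* = 5: −0.10 × 5 = −0.5 points
- *D* = 8: −0.10 × 8 = −0.8 points

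Against the 3-point target in section 6.5, these are 0.5/3 = 17% and 0.8/3 = 27%. The minus sign means that the contrast moves against the intervention: losing low-scoring controls raises the control mean. If the removed children scored higher, the sign would reverse.

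**The case against.** **The rule is permissive.** It says may, and an investigator might never use it. Some families who miss visits would lack a 12-month Bayley in any case. This stands. The documents support that the rule could create or worsen differential loss, not that it would.

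**The section 6.3 promise is about clinical contacts.** It does not mention study visits, so the clash is not word for word. This also stands. The tension rests on that promise read together with sections 3.1.1 and 5.1.2.1.

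**The analysis plan already handles dropout.** The formula above describes an unadjusted completer comparison, whereas section 6.3 plans imputation, dropout predictors and sensitivity analyses. These lessen the harm. They cannot recover outcomes that are no longer collected, and the SAP does not carry them forward.

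**EI outcomes may be safe.** Section 4.6 does not say that agency data stop. That is correct. The gap is that it does not say they continue.

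Four stronger readings are tempting, and the documents do not support them:

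- *That the county exclusion is a second removal rule.* A reader might infer that it can bite only after enrolment, because residence is already an inclusion criterion. But the exclusion section closes with "Subjects that do not meet all of the enrollment criteria may not be enrolled", which ties the criteria to enrolment. Section 3.4 treats county as an eligibility matter, and the sub-study exclusion lists also restate inclusion criteria in the negative. No text removes later movers or links moving to arm.
- *That 28% versus 6% loss is planned and removals would come on top.* Those rates are back-calculated from 130 and 170 and contradict the stated doubling. Nothing shows that investigator discontinuations fall outside the dropout allowed for in section 6.5, so adding them could double-count.
- *That the as-randomised analysis contradicts section 4.6.* It fixes the arm in which a child is analysed, not whether an outcome is collected.
- *That the rule would favour the intervention.* With low-scoring controls removed, the shift runs the other way.

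**Conclusion.** The point holds for the missed-visit rule. Section 4.6 allows discontinuation from the study without preserving outcome collection, section 4.6.1 does not fill the gap, and both are in tension with sections 3.1.1, 5.1.2.1 and 6.3. The link to arm rests on the protocol's own expectation in section 6.5 about dropout in general. No document shows that removals would fall mainly on controls.

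The shift of 0.5 to 0.8 points per 10 percentage points of excess control loss is an illustration under assumed inputs, for an unadjusted completer comparison. It shows that avoidable removals could matter against a 3-point target; it is not a forecast. The county item is only an ambiguity of wording.

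**What to change.** - **Reconcile sections 4.6 and 4.6.1 with 3.1.1 and 6.3.** Remove visit non-adherence as a ground for ending outcome follow-up. State that the Bayley, within the age limit already allowed, and the EI agency data under the signed release are still collected unless consent is withdrawn.
- **Say the same in the SAP,** and report discontinuations by arm and reason. If follow-up has already ended, this report and any agency data still obtainable under the release are what remain.
- **As a separate clarification,** word the county exclusion in 3.4.2.1 as residence at enrolment, and state that children who move later stay in the analysis as randomised.

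The cost is a few sentences of amendment and some added effort to track families. For later movers, the EI data source is the Philadelphia programme, so the text should also say what is collected on EI use after a move.

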### 4.6.1 Early Termination Study Visit

Subjects who withdraw from the study following screening may receive recommendations for follow up per their specific needs, including a referral to daycare or Early Head Start programs.

## 5 STUDY EVALUATIONS AND MEASUREMENTS

### 5.1 Screening and Monitoring Evaluations and Measurements

#### 5.1.1 Medical Record Review

- Date of birth, Chart Review, History, Demographics
- Gestational age, sex, problem list, developmental assessments

#### 5.1.2 Other Evaluations, Measures

##### 5.1.2.1 Main RCT

Following written informed consent, participant families will complete a baseline visit. Measures of demographic and biological variables (child age, sex, race/ethnicity, family income, maternal education level, and family structure), parental health literacy, and the home environment will be collected by research staff blinded to randomization assignment at this visit (Table 3). The Short Assessment of Health Literacy (SAHL, Appendix 3) is a validated 18-item measure of health literacy in both English and Spanish. The SAHL has good reliability ( $\alpha=0.80$  and 0.89) in Spanish- and English-speaking samples, and correlated well with other measures of health literacy including the REALM ( $r=0.94$ ,  $p<0.05$ ) and TOFHLA ( $r=0.68$ ,  $p<0.05$ ). SAHL scores  $\leq 14$  have been used to categorize low health literacy. The StimQ (Appendix 4) is a validated parent self-report questionnaire designed to measure cognitive stimulation provided in the home for children ages 5 to 72 months of age. The StimQ contains 4 subscales (availability of learning materials, reading, parental involvement in developmental advance, parental verbal responsiveness) and is available in English and Spanish. Internal consistency (Cronbach  $\alpha=0.88-0.93$ ) and test-retest reliability ( $ICC=0.93$ ) of the StimQ is excellent, and it correlates well ( $r=0.55$ ) with the IT-HOME Inventory, another measure of the home environment. Poverty will be assessed by

examining family income (<100% of the Federal Poverty Level) and maternal education status ( $\leq$  High School).

Measures of engagement will be collected at baseline and at follow-up visits every 3months, while EI referral and service use will be collected at follow-up visits every 3 months. In addition, public policy changes that may impact access to services (e.g. changes in EI funding or eligibility) will be queried of EI staff throughout the study period. The visits will be conducted by research staff blinded to randomization assignment by telephone or email at the discretion of the parent. The Client Engagement in Child Protective Services (CECPS, Appendix 1) is a validated 14-item measure of parent engagement in child welfare services and contains 4 subscales: receptivity, working relationship, buy-in, and mistrust Reliability was good ( $\alpha=0.95$  for the total score and  $\alpha=0.81-0.91$  for subscale scores), and correlation with measures of global engagement and helping relationships and personal support was moderate to strong ( $r=0.36$  to  $0.78$ ). Following discussions with the author of the CECPS (personal communication with [name]), the CECPS will be adapted for an EI population by conducting semi-structured interviews and cognitive testing with a separate group of parents previously referred to EI from one of the urban practices to identify new items and refine the wording on existing items. The adaption of the CECPS measure will be carried out as part of a separate study (IRB 18-014884). We have previously adapted an engagement measure for ADHD using a similar process (See Appendix). Parents will be asked at study visits to complete the adapted CECPS, which we are referring to as the EI Engagement questionnaire, and measures of completion of EI referrals (intake, registration, assignment of service coordinator, home visit, and MDE), eligibility for and initiation of EI services (IFSP), EI services use if eligible (number of EI service visits and duration of EI service visits), and use of other services (transfer to Preschool EI services, childcare or preschool enrollment). We will corroborate parent-reported visits with EI staff.

Finally, all children will be assessed for developmental status at 12 months following enrollment. Children will either attend, the Seashore House at CHOP with the Center for Human Phenomic Science or the Roberts Center for Pediatric Research with a clinician, to complete The Bayley Scales of Infant and Toddler Development- third edition (Bayley-III) (Appendix 5) is a validated scale of infant and toddler development from 1 to 42 months of age. The Bayley-III has good reliability and correlates well with other measures of development including the Wechsler Preschool and Primary Scale of Intelligence, third edition ( $r=0.83$ ). The Bayley-III has three subscales that will be utilized (cognitive, motor, and language) and a measure of socioemotional development.

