## **3.2 Allocation to Treatment Groups and Blinding**

In this study, 360 eligible children will be randomized 1:1 to the FN or usual care consisting of routine Child Find procedures. We chose a randomized design, because it is most effective at guarding against bias and will ensure that patients in both arms are similar in observed and unobserved characteristics. The initial randomization will be stratified by practice site, child sex, and age group (0-<18 months old and 18-30 months old) to ensure

balance between groups. We will control post-hoc statistically for any imbalances that arise. Allocation concealment (blinding of the treatment assignment) will be implemented using sealed, opaque envelopes, along with stratification, and randomly permuted blocks of unequal sizes (to prevent providers and patients from manipulating the randomization). Treatment assignment will be done at the time of enrollment following informed consent and patients will be followed over time with measures related to EI referral completion, EI services completion, and patient engagement collected at baseline, 3, 6, 9, and 12 months as well as child developmental status around 12 months.

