### **9 STUDY ADMINISTRATION**

#### **9.1 Treatment Assignment Methods**

##### **9.1.1 Randomization**

Children and their parents will be randomized following informed written consent 1:1 to 1) a family navigator trained in the Opening Doors to Early Intervention program or 2) usual

---

care. Children will be stratified by practice site, age group (<18 months, 18-30 months old), and sex and randomized in blocks of 10-15 using randomly generated study numbers. Sealed opaque envelopes containing treatment assignments will be produced by the study biostatistician. Children and their parents will participate in the study over a 12-month period with data collection occurring at baseline, 3 months, 6 months, 9 months, and 12 months.

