### **9.1.2 Blinding**

Allocation concealment (blinding of the treatment assignment) will be implemented using sealed, opaque envelopes, along with stratification, and randomly permuted blocks of unequal sizes (to prevent providers and patients from manipulating the randomization). Participants will not be blinded to their treatment assignment. However, research will be blinded to treatment assignment when collecting study data.

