### **9.5 Recruitment Strategy**

#### **9.5.1 Main RCT: Subjects**

Recruitment will be conducted through the Pediatric Research Consortium (PeRC). Eligible children and their parents will be identified at the time of a clinical encounter (visit or telephone) involving a referral to EI through the use of an EHR recruitment prompt. Parents who verbally agree to be contacted will have their contact information sent to research staff. Medical records of the potentially eligible subjects will be screened and assessed for eligibility prior to contacting the subject. Subsequent to screening the medical record, the subject will be called by the research staff to explain the study and arrange for a study visit that will be completed either in person or remotely. Research staff will briefly explain the study procedures, guided by the information set forth in the approved consent form. This includes reading the inclusion criteria to the potential participant, and asking whether or not this individual is interested in participating. Research staff will then schedule a time to either meet with the parent in person or to complete the baseline visit remotely. In the event that the baseline visit is scheduled to be completed remotely, research staff will also need to confirm the subject's email address in order to send them the electronic Informed Consent Form via REDCap. At this visit, parents will be asked to provide written informed consent (which can be completed in person or remotely by utilizing the electronic REDCap e-consent process) to participate in the study and to sign, either in person or electronically, a Medical Release of Information form to enable the research team to obtain EI data from Philadelphia Infant Toddler Early Intervention. The consent and Medical Release of Information form will be administered by a trained member of the research staff either in person or remotely and will consist of all elements of informed consent.

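### The protocol does not require StimQ, EI Engagement and SAHL to be completed before randomisation or before the parent learns the arm

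*Protocol*

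**What the plan says.** Protocol section 4.1.1 lists the contents of the enrolment visit. After record review and eligibility the list runs "Informed Consent - Randomization - Measures of the following: - Demographics - EI Engagement", followed by StimQ and SAHL.

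Section 3.2 states: "Treatment assignment will be done at the time of enrollment following informed consent". Section 9.1.1 likewise states: "Children and their parents will be randomized following informed written consent 1:1". Section 9.5.1 places consent at the baseline visit itself: "At this visit, parents will be asked to provide written informed consent". Assignments are held in sealed opaque envelopes. The documents do not say when in the visit the envelope is opened, who opens it, or when the parent is told.

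On blinding, section 9.1.2 states: "Participants will not be blinded to their treatment assignment". Section 5.1.2.1 says that the baseline measures "will be collected by research staff blinded to randomization assignment at this visit". The same section describes StimQ as one that "is a validated parent self-report questionnaire designed to measure cognitive stimulation provided in the home", and has parents complete the EI Engagement questionnaire.

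Table 1 and section 4.1.1 allow SAHL, although a baseline measure, to be completed at a later follow-up visit when the baseline visit is remote.

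**The concern.** A baseline covariate or moderator is safe to use because treatment cannot have influenced it. A parent-reported score loses that protection once the parent knows the arm. A parent just told that a navigator will help with early intervention may describe reading, play or willingness to engage differently from one told to expect usual care. Blinding the person who records the answer does not prevent this.

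Three planned uses are exposed:

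- StimQ is an effect modifier in Protocol section 6.4.2.3 and an adjustment covariate in SAP Aim 3a.
- Baseline characteristics are compared by arm (section 6.4.1), and imbalances may be adjusted for, including in the primary Bayley-III cognitive model (sections 3.2, 6.3 and 6.4.2.1). A shift caused by knowing the arm would look like chance imbalance and could trigger an adjustment that introduces bias.
- SAHL is the Aim 3b moderator. If taken at a follow-up visit, it comes after randomisation and possibly after months of navigator contact, which includes education (section 7.1.1).

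**Working it through.** The plan gives no figure to reproduce; the check is of procedural order.

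1. **Order of steps.** Section 4.1.1 is the only place that names randomisation and the measures in one list, and randomisation comes first. Table 1 has no randomisation row. Sections 3.2 and 9.1.1 fix assignment only relative to consent. Sections 3.1.1 and 5.1.2.1 also fix the baseline visit only relative to consent. Those four sections therefore leave the order of measures and assignment open.

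2. **Any safeguard.** No section makes completed measures a precondition for opening the envelope. Section 7.1.1 puts first navigator contact at the start of the study without placing it before or after StimQ.

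3. **Who could be influenced.** Collectors are blinded and parents are not. StimQ and EI Engagement come from the parent. SAHL is described as interactive, so for it the issue is mainly timing after assignment rather than self-report.

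4. **Which analyses use the scores.** StimQ and SAHL are used in Aim 3. The baseline engagement score is not used in Aim 2: section 6.4.2.2 takes engagement at 3, 6, 9 and 12 months as mediator, and SAP Aim 2 takes the 3-month score. The unadjusted primary comparison uses none of them.

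5. **Why no size can be stated.** Suppose knowing the arm shifts reported StimQ by d in the intervention arm, and b is the slope of the cognitive score on StimQ. In a linear model without an interaction, adjusting for StimQ moves the estimated arm effect by −b × d. With an arm-by-StimQ interaction g, a uniform shift leaves g unchanged and moves the arm effect at a given StimQ score by −(b + g) × d. The interaction itself is distorted only if the shift varies with the true StimQ level, or if arm awareness makes the score noisier. The documents give none of b, d or g.

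6. **Design figures.** The sample size (360 recruited, 300 evaluable) and stated power (96% for the primary outcome, 84% for moderation) do not depend on the order of steps.

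**The case against.** The strongest reply is that section 4.1.1 is an unnumbered list of visit contents, not a timeline. It includes SAHL, which may be done months later. Measures could fall between consent and assignment without contradicting sections 3.2, 5.1.2.1 or 9.1.1, and staff blinding at baseline fits an unopened envelope at least as well as a disclosed arm. Same-visit contamination of StimQ could arise almost only through reporting, since the home has had no time to change. StimQ serves an exploratory aim, and section 5.1.2.1 reports a test-retest ICC of 0.93.

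Much of this stands, and it limits the point. A reader might infer three stronger things that the documents do not support:

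- **That parents do answer knowing their arm.** Section 9.1.2 says they are not blinded, not when they are told.
- **That several sections independently confirm randomisation before measurement.** Only the order in section 4.1.1 points that way; sections 3.2 and 9.1.1 are merely compatible with it.
- **That the Aim 2 engagement path is biased by a calculable amount.** Assuming a 0.1 to 0.3 SD shift and a 0.5 correlation gives 0.1 × 0.5 = 0.05 to 0.3 × 0.5 = 0.15 SD. That would apply only to an adjustment for baseline engagement, which neither document plans.

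The reply does not supply the missing safeguard. Staff who follow the list as printed would randomise first, and nothing tells them otherwise. Nor does it answer the explicit SAHL allowance. Test-retest reliability does not show that parents are unaffected by knowing their arm.

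**Conclusion.** The point holds as a gap in the procedure. The protocol does not secure measurement before assignment or disclosure, and its only listed order puts assignment first. The consequence is a risk to StimQ in Aim 3a and to any parent-reported baseline characteristic drawn into imbalance adjustment. For SAHL in Aim 3b, measurement after randomisation is expressly permitted.

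No magnitude can be derived. The unadjusted comparison of Bayley-III cognitive scores is unaffected; the primary model is exposed only if an affected score is added as a covariate. This is a minor point, worth acting on because the remedy is nearly free. It assumes that the envelope may be opened, and the parent told, during the baseline visit, which the documents allow but do not state.

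**What to change.** In Protocol sections 4.1.1, 3.2 and 9.1.1, place randomisation after the baseline measures. Require demographics, StimQ, EI Engagement and, where possible, SAHL to be complete before the envelope is opened. Record the time of each measure and the time of assignment. Section 3.1.1 omits engagement from the baseline measures, whereas Table 1 and sections 3.2, 4.1.1 and 5.1.2.1 include it; reconcile these.

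In the SAP, flag any StimQ, SAHL or engagement score taken after assignment, bar flagged scores from imbalance-driven adjustment, and run the Aim 3b moderator analysis with and without post-assignment SAHL scores.

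The cost is a reordering within one visit, two recorded times and one sensitivity analysis, with no added procedure. The documents do not give enrolment status. If enrolment is complete, the SAP changes can still be made wherever the actual order can be recovered, and that order should be reported.
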